## **11. Statistical Methods and Determination of Sample Size**

### **11.1. Statistical Analysis Plan and General Statistical Methods**

All data will be handled and processed according to the sponsor's representative (Novotech [Australia] Pty Ltd) SOPs, which are written based on the principles of GCP.

A Statistical Analysis Plan (SAP) containing the detailed planned statistical methods will be finalized prior to locking of the study database for the interim and final analysis and will form the basis for the programming of the displays and analyses of the final study data. All statistical calculations will be performed using SAS® (SAS Institute Inc., Cary, NC, USA) or similar software.

The statistical analyses will consist of both inferential and descriptive statistics. In general, the data will be presented by dose group. All collected and derived data will be included in the patient data listings.

All inferential analyses will be conducted at a one-sided 0.05 level of significance. Unless otherwise specified, all inferential testing will be one-sided in nature.

Continuous data, other than PK data, will be summarized by treatment group and time point using the number of observations, arithmetic mean, standard deviation, median, minimum and maximum. The coefficient of variance, geometric means and geometric coefficient of variance will also be presented for the concentration-related PK data. Categorical data will be summarized by the number and percentage of patients in each category. Unless specifically stated otherwise, the number of patients in the treatment group (for the specific analysis set) will be used as the denominator for all percentage calculations.

Baseline is defined as the last available non-missing value collected prior to the first administration of IP.

Change from baseline values will be calculated as the difference between the result at a specific time point, and the baseline value for the specific endpoint.

Missing, unused, or spurious data will be handling in the following manner:

- There will be no imputations or substitution made for missing safety data points.
- For the PK analyses, imputations will be made for missing data points.

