### **11.3.3. Efficacy Analyses**

All Efficacy analyses will be based on the ITT set unless otherwise specified. All efficacy data will be summarised by study visit and treatment group.

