3.1 General Considerations

All data collected on the electronic case report form (eCRF) will be presented in the data listings and will be listed and sorted by treatment arm, participant number and visit, where applicable. All descriptive summaries will be presented by treatment group and nominal visit/time point (where applicable).

Unless otherwise stated, the following methods will be applied:

- Continuous variables: Descriptive statistics will include the number of non-missing values (n), arithmetic mean, standard deviation (SD), median, minimum and maximum values.

The minimum and maximum values will be displayed to the same decimal precision as the source data, the arithmetic mean, SD and median values will be displayed to one more decimal than the source data for the specific variable.

95% Confidence Intervals (CIs), mean differences (among treatments and from baseline) and least-square (LS-Means) values will be displayed to one more decimal than the source data for a specific variable. P-values will be displayed to 3 decimal places.

The appropriate precision for derived variables will be determined based on the precision of the data on which the derivations are based, and statistics will be presented in accordance with the above-mentioned rules.

- Figures based on continuous summary data:
 - X-axis will represent the linear scheduled time expressed as -Day x for screening values and +Day y on treatment values
 - Y-axis will represent the Mean (+/-SD) and be presented as box-plots (median interquartile) parameter value (unit).
- Categorical variables: Descriptive statistics will include counts and percentages per category. The denominator in all percentage calculations will be the number of participants in the relevant analysis population with non-missing data, unless specifically stated otherwise. Percentages will be displayed to one decimal place. Proportions will be displayed to 3 decimal places.

95% Confidence Intervals (CIs), difference in proportions, odds ratio's and other categorical parameters will be displayed to one decimal place for percentages. Proportions will be displayed to 3 decimal places. P-values will be displayed to 3 decimal places.

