- Repeat/unscheduled assessments: Only values collected at scheduled study visits/time points will be presented in summary tables. If a repeat assessment was performed, the result from the original assessment will be presented as the result at the specific visit/time point. All collected data will be included in the data listings.
- Assessment windows: All assessments will be included in the data listings and no visit windows will be applied to exclude assessments that were performed outside of the protocol specified procedure windows.
- Result display convention: Results will be center aligned in all summary tables and listings. Participant identifiers visit and parameter labels may be left-aligned if required.
- Date and time display conventions: The following display conventions will be applied in all outputs where dates and/or times are displayed:

Date only: YYYY-MM-DD

Date and time: YYYY-MM-DD HH:MM

If only partial information is available, unknown components of the date or time will be presented as 'NK' (not known), i.e., '2016-NK-NK'. Times will be reported in military time.

- End of Study (EoS) vs Early Termination (ET)

For any analyses based on safety data, efficacy and PD data, EOS and ET assessment will be summarized separately.

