3.2 Key Definitions

The following definitions will be used:

- **Baseline:** The baseline value is defined as the last available valid (quantifiable continuous or categorical value), non-missing observation for each participant prior to first study drug administration. Repeat and unscheduled assessments will be included in the derivation of the baseline values.

For HBsAg, ALT, AST, ALP, and total Bilirubin (TBL), the baseline value is defined as the average of screening and day 1 pre-dose.

For HBeAg, the Baseline value is value taken at screening visit.

- **Change from Baseline:** The change from baseline value is defined as the difference between the result collected/derived at a post-baseline visit/time point and the baseline value.

The change from baseline value at each post-baseline visit/time point will be calculated for all continuous parameters using the following formula:

$$\text{Change from Baseline Value} = \text{Result at Visit/Time Point} - \text{Baseline Value}$$

The change from baseline value will only be calculated if the specific post-baseline visit/time point result and the baseline value for the parameter are both available and will be treated as missing otherwise.

- **Percent Change from baseline:** The percent change from baseline at each post-baseline visit/time point will be calculated for all continuous parameters using the following formula:

$$\% \text{ Change from Baseline} = 100 \times [(\text{Post-Dose Visit Value} - \text{Baseline}) / \text{Baseline}]$$

- **Study day:** The study day of an event is defined as the relative day of the event starting with the date of the first study drug administration (reference date) as Day 1 (there will be no Day 0).

The study day of events occurring before the first study drug administration will be calculated as:

$$\text{Study Day} = (\text{Date of Event} - \text{Date of First Study Drug Administration})$$

For events occurring on or after Day 1, study day will be calculated as:

$$\text{Study Day} = (\text{Date of Event} - \text{Date of First Study Drug Administration}) + 1$$

Study days will only be calculated for events with complete dates and will be undefined for events that are 'Ongoing' at the end of the study.

Relative days compared to an alternative reference point will be calculated similarly, but the alternative starting reference start date will be used instead of the date of the first study drug dosing.

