HBV Genotype	A	xx (xx.x%)	xx (xx.x%)	xx (xx.x%)
	B	xx (xx.x%)	xx (xx.x%)	xx (xx.x%)
	C	xx (xx.x%)	xx (xx.x%)	xx (xx.x%)
	D	xx (xx.x%)	xx (xx.x%)	xx (xx.x%)
	E	xx (xx.x%)	xx (xx.x%)	xx (xx.x%)
	F	xx (xx.x%)	xx (xx.x%)	xx (xx.x%)
	G	xx (xx.x%)	xx (xx.x%)	xx (xx.x%)
	H	xx (xx.x%)	xx (xx.x%)	xx (xx.x%)
	I	xx (xx.x%)	xx (xx.x%)	xx (xx.x%)
	J	xx (xx.x%)	xx (xx.x%)	xx (xx.x%)
Audit-C overall score	n	xx	xx	xx
	Mean	xx.x	xx.x	xx.x
	SD	xx.x	xx.x	xx.x
	Median	xx.x	xx.x	xx.x
	Minimum	xx	xx	xx
	Maximum	xx	xx	xx

Source Listing: 16.2.4.1

SD: Standard Deviation. Percentages are calculated (the denominator used for the calculation) based on the number of participants in the ITT Set in each treatment group (N).

*For childbearing potential, percentages are based on the number of female participants.

Programming note:

- Repeat for table 14.1.2.2 (mITT Set), table 14.1.2.3 (Safety Set) and table 14.1.2.4 (PP Set)

Table 14.1.3.x Summary of Viral Serology at Screening (ITT set)

Parameter	Category	Group 1 (N=xx)	etc.	Group x (N=xx)
Hepatitis D virus (anti-HDV)	n	xx	xx	xx
	Positive	xx (xx.x%)	xx (xx.x%)	xx (xx.x%)
	Negative	xx (xx.x%)	xx (xx.x%)	xx (xx.x%)
Antibody to HIV (anti-HIV)	n	xx	xx	xx
	Positive	xx (xx.x%)	xx (xx.x%)	xx (xx.x%)
	Negative	xx (xx.x%)	xx (xx.x%)	xx (xx.x%)
Antibody to HCV (anti-HCV),	n	xx	xx	xx
	Positive	xx (xx.x%)	xx (xx.x%)	xx (xx.x%)
	Negative	xx (xx.x%)	xx (xx.x%)	xx (xx.x%)
PCR-based Quantitative HCV Viral Load *	n	xx	xx	xx
	Positive	xx (xx.x%)	xx (xx.x%)	xx (xx.x%)
	Negative	xx (xx.x%)	xx (xx.x%)	xx (xx.x%)
Anti-HBs	n	xx	xx	xx
	Positive	xx (xx.x%)	xx (xx.x%)	xx (xx.x%)
	Negative	xx (xx.x%)	xx (xx.x%)	xx (xx.x%)
Anti-HBe	n	xx	xx	xx
	Positive	xx (xx.x%)	xx (xx.x%)	xx (xx.x%)
	Negative	xx (xx.x%)	xx (xx.x%)	xx (xx.x%)

Source Listing: 16.2.4.5

SD: Standard Deviation. Percentages are calculated (the denominator used for the calculation) based on the number of participants in the ITT Set in each treatment group (N).

*For PCR-based Quantitative HCV Viral Load, percentages are based on the number of anti-HCV positive participants.

Table 14.1.3.x Summary of Viral Serology at Screening (ITT set)

Parameter	Category	Group 1 (N=xx)	etc.	Group x (N=xx)
Quantitative HBsAg Level	n	xx	xx	xx
	Mean	xx.x	xx.x	xx.x
	SD	xx.x	xx.x	xx.x
	Median	xx.x	xx.x	xx.x
	Minimum	xx	xx	xx
	Maximum	xx	xx	xx
Second Quantitative HBsAg Level	n	xx	xx	xx
	Mean	xx.x	xx.x	xx.x
	SD	xx.x	xx.x	xx.x
	Median	xx.x	xx.x	xx.x
	Minimum	xx	xx	xx
	Maximum	xx	xx	xx

Source Listing: 16.2.4.5

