LS mean is derived from a general linear model for repeated measures. The covariates are treatment groups, visit, baseline HBsAg, A Genotype, HBeAg positive and the interaction term of treatment group*visit.

Covariance structure is XXX.

CI = Confidence Interval. SE = Standard Error.

Programming Note:

- Repeat for table 14.2.2.1.2 (ITT set with no imputation), 14.2.2.2.1 (mITT with imputation), 14.2.2.2.2 (mITT with no imputation), 14.2.2.3.1 (PP set with imputation) and 14.2.2.3.2 (PP set with no imputation) .

-The SAS code used to implement this analysis is given below:

```
PROC MIXED DATA=dataset;
  CLASS ID TRT VISIT HBeAg;
  MODEL CHG = Baseline HBeAg TRT VISIT TRT*VISIT / SOLUTION CL;
  DDFM=KenwardRoger;
  REPEATED VISIT /SUBJECT = ID TYPE = UN ;
  LSMEANS TRT*VISIT / DIFF CL;
  RUN;
```

Table 14.2.3.1 Summary and Analysis of HBsAg Loss Rate A (ITT Set)

Visit	Category	Statistics	EYP001a 200 mg QD + NA daily (N=XXX)	Placebo + NA daily (N=XXX)
Week 16		n	xx	xx
	HBsAg Loss	n (%) [1]	xx (xx.x %)	xx (xx.x %)
		p-value	0.XXX	

<Repeat for Week 40>

Source Listing: 16.2.6.1

p-value is based on the Person Chi-squared Test.

HBsAg Loss is defined as HBsAg value < LLOQ/TND.

[1] Number of subjects at each visit (Visit n) will be used as the denominator for the calculation of all percentages.

Programming Note:

- Only present Week 16 and Week 40 will consider multiplicity by a combination of a hierarchical fixed test procedure and a Hochberg procedure to adjust p-value.

Table 14.2.3.2 Summary and Analysis of HBsAg Loss Rate B (ITT Set)

Visit	Category	Statistics	EYP001a 200 mg QD + NA daily (N=XXX)	Placebo + NA daily (N=XXX)
Week 16		n	xx	xx
	HBsAg Loss	n (%) [1]	xx (xx.x %)	xx (xx.x %)
		p-value	0.XXX	

<Repeat for Week 40>

Source Listing: 16.2.6.1

p-value is based on the Person Chi-squared Test.

HBsAg Loss is defined as HBsAg value < LLOQ/TD.

[1] Number of subjects at each visit (Visit n) will be used as the denominator for the calculation of all percentages.

Programming Note:

- Only present Week 16 and Week 40 will consider multiplicity by a combination of a hierarchical fixed test procedure and a Hochberg procedure to adjust p-value.

Table 14.2.4.1 Summary and Analysis of HBsAg Responder Rate A (ITT Set)

Visit	Category	Statistics	Decrease from Baseline \geq 1.0 on the log10 Scale	
			EYP001a 200 mg QD + NA daily (N=XXX)	Placebo + NA daily (N=XXX)
Week 16	HBsAg Responder	n		
		n (%) [1]		
		p-value		
Week 40		n	xx	xx

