		n (%) [1]	xx (xx.x %)	xx (xx.x %)
		p-value	0.XXX	

Source Listing: 16.2.6.1

p-value is based on the Person Chi-squared Test.

[1] Number of subjects at each visit (Visit n) will be used as the denominator for the calculation of all percentages.

Programming Note:

- Only to present Week 16 and Week 40 will consider multiplicity by a combination of a hierarchical fixed test procedure and a Hochberg procedure to adjust p-value.

Table 14.2.4.2 Summary and Analysis of HBsAg Responder Rate B (ITT Set)

Visit	Category	Statistics	Decrease from Baseline \geq 0.5 on the log10 Scale	
			EYP001a 200 mg QD + NA daily (N=XXX)	Placebo + NA daily (N=XXX)
Week 16	HBsAg Responder	n	xx	xx
		n (%) [1]	xx (xx.x %)	xx (xx.x %)
		p-value	0.XXX	
Week 40		n	xx	xx
		n (%) [1]	xx (xx.x %)	xx (xx.x %)
		p-value	0.XXX	

Source Listing: 16.2.6.1

p-value is based on the Person Chi-squared Test.

[1] Number of subjects at each visit (Visit n) will be used as the denominator for the calculation of all percentages.

Programming Note:

- Only to present Week 16 and Week 40 will consider multiplicity by a combination of a hierarchical fixed test procedure and a Hochberg procedure to adjust p-value.

Table 14.2.5 Summary of HBsAg Relapse Rate (ITT Set)

Visit	Category	Statistics	Group 1 (N=XXX)	etc.	Group x (N=XXX)
Week 16		n	xx	xx	xx
	HBsAg Relapse	n (%) [1]	xx (xx.x %)	xx (xx.x %)	xx (xx.x %)
<Repeat for Week 20, 28, 40>		n	xx	xx	xx
	HBsAg Relapse	n (%) [1]	xx (xx.x %)	xx (xx.x %)	xx (xx.x %)

Source Listing: 16.2.6.1

HBsAg Relapse is defined as patients who became negative [HBsAg < LLOQ], then increased with HBsAg > LLOQ.
 [1] Number of subjects at each visit (Visit n) will be used as the denominator for the calculation of all percentages.

Table 14.2.6 Summary of Virologic Failure Rate of HBV DNA (ITT Set)

Visit	Category	Statistics	Group 1 (N=XXX)	etc.	Group x (N=XXX)
Week 16		n	xx	xx	xx
	Virologic Failure Rate	n (%) [1]	xx (xx.x %)	xx (xx.x %)	xx (xx.x %)
<Repeat for Week 20, 28, 40>		n	xx	xx	xx
	Virologic Failure Rate	n (%) [1]	xx (xx.x %)	xx (xx.x %)	xx (xx.x %)

Source Listing: 16.2.6.2

Virologic Failure Rate of HBV DNA is defined as patients with a confirmed quantifiable HBV DNA increase of $\geq 1\log_{10}$ HBV DNA copies/mL above LLOQ.
 [1] Number of subjects at each visit (Visit n) will be used as the denominator for the calculation of all percentages.

Table 14.2.7 Summary of HBV-pgRNA (ITT Set)

Visit	Group 1 (N=XXX)		etc.		Group x (N=XXX)	

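### The SAP's ITT-titled tables for HBsAg response and loss divide by visit n instead of the protocol's ITT N, undeclared in Section 15, and the protocol's zero-change sensitivity t-test appears in no SAP analysis

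*SAP*

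**What the plan says.** **Denominator.** Protocol 11.1 sets the default: "the number of patients in the treatment group (for the specific analysis set) will be used as the denominator for all percentage calculations". It allows exceptions where stated, and the protocol states none for these endpoints. Protocol 11.3.3 adds: "All Efficacy analyses will be based on the ITT set unless otherwise specified". Section 11.2.1 defines that set as everyone randomised.

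SAP 3.1 uses instead the "number of participants in the relevant analysis population with non-missing data, unless specifically stated otherwise". The four key secondary shells (HBsAg loss A and B, Tables 14.2.3.1 and 14.2.3.2; responder A and B, Tables 14.2.4.1 and 14.2.4.2) are all titled for the ITT set and carry the footnote "Number of subjects at each visit (Visit n) will be used as the denominator for the calculation of all percentages". The SAP's own demographic shells (14.1.2.x) divide by ITT N.

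**Patients without a value.** SAP 3.2 computes a change only if the visit result and "the baseline value for the parameter are both available and will be treated as missing otherwise". On early termination, SAP 3.1 says: "For any analyses based on safety data, efficacy and PD data, EOS and ET assessment will be summarized separately". Multiple imputation (SAP 3.5) is for the primary HBsAg data, and SAP 18 lists imputed versions only of the HBsAg level tables (14.2.1 and 14.2.2 series).

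**Primary endpoint.** Protocol 11.3.3.1 plans a Week 16 t-test with missing change set to zero, as a sensitivity analysis. SAP 3.3 plans the repeated-measures model on ITT, mITT and PP, each with MI and without imputation. No t-test appears in SAP 3.3, 12.1 or 18.

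**Declared changes.** SAP 15 says that MI under MAR replaces the zero-change handling of protocol 11.3.3.1. It does not say that this handling was a sensitivity t-test, and it does not mention percentage denominators.

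**The concern.** A patient who leaves before Week 16 or Week 40 stays in the denominator under the protocol and leaves it under the SAP. If such patients are mostly non-responders and mostly on active treatment, the SAP's rate on active rises without any additional responder, in a table still labelled ITT. These four endpoints are formally tested under Hochberg, so the choice could move a test decision. It is also a departure from the protocol that the SAP's list of departures omits.

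For the primary endpoint, the protocol had one analysis that was deliberately unfavourable to missing patients. Without it, a reader cannot see whether the result depends on MAR.

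**Working it through.** **1. The plan's own figure.** Protocol 11.4.1 and SAP 2.4 dilute the planned effect for zero change in 10% dropouts: 1.0 × 0.9 = 0.9, with SD 1.08, one-sided alpha 0.05, 80% power and 3:1 allocation. Noncentral-t power with noncentrality 0.9 / (1.08 × √(1/n₁ + 1/n₀)) is 80.1% for N=49 at an exact 3:1 split and 79.6% at 37:12. The stated 49 reproduces. It rests on a zero-change assumption that no planned SAP analysis now applies. At 37:12 the undiluted effect of 1.0 has 86.5% power.

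**2. Does the Pearson test use visit n?** The footnote governs percentages only. A patient with no Week 16 value has no change score (SAP 3.2), no ET value carried into the visit (SAP 3.1) and no imputed status (SAP 18). Nothing supplies a responder or loss status, so dropping the patient from the test is the natural inference. It is not stated.

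**3. Which Hochberg level applies?** Entry requires HBsAg above 100 IU/mL, and values below LLOQ are set to 0.04 or 0.015 IU/mL (SAP 3.2). A loss from 100 to 0.04 is log₁₀(2500) = 3.4 log₁₀. So every loss is also a response at 1.0, and every response at 1.0 is one at 0.5. With no placebo events, p falls as the active count rises. The two loss endpoints therefore take the 0.05 and 0.025 steps. Unless loss is also common, responder A is decided at 0.05/3 = 0.017 and responder B at 0.05/4 = 0.0125.

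**4. Size at those levels.** One-sided Pearson with x events of n₁ on active and none of n₀ on placebo:

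z = (x/n₁) / √[p̄(1−p̄)(1/n₁ + 1/n₀)], with p̄ = x/(n₁+n₀).

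Example, 10/37 v 0/12: p̄ = 10/49 = 0.204; z = 0.2703/0.1339 = 2.019; p = 0.0218. For 10/33 v 0/12: p̄ = 10/45 = 0.222; z = 0.3030/0.1401 = 2.162; p = 0.0153.

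The dropout counts are assumptions: 10% of 37 is 3.7, taken as 4, and 10% of 12 is 1.2, taken as 1. All dropouts are taken as non-responders.

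| Events on active | Level | ITT N (37 v 12) | Visit n, 4 active missing (33 v 12) | Visit n, 4 active and 1 placebo missing (33 v 11) |
|---|---|---|---|---|
| 10 | 0.017 | 0.022 | 0.015, crosses | 0.019 |
| 11 | 0.0125 | 0.016 | 0.011, crosses | 0.0135 |
| 4 (loss, near the planned 10%) | 0.05 | 0.117 | 0.103 | 0.113 |

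Exact enumeration of a single test at the 0.0125 level, with a true ITT response rate of 20% in both arms, gives rejection of 0.34% on ITT N v 0.76% on visit n with 4 active-only dropouts. With 4 active and 1 placebo missing it is 0.33% v 0.34%.

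**5. MAR.** MI assumes it. The repeated-measures model without imputation is valid only under it. mITT requires a Week 16 assessment and PP is a subset of mITT, so both leave out the patients in question. None of the six primary analyses departs from MAR.

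**The case against.** The strongest reply is about consequence. The non-missing denominator is openly stated in SAP 3.1 and in each shell, and the shells print both N and n, so a reader could recompute. The Week 16 family is tested only if the primary is significant. This is an exploratory Phase 2a study and these are secondary endpoints. All of that stands and limits the weight of the point. It does not remove the mismatch with the protocol, and the test decision would still rest on the printed p-value. For Week 40, SAP 3.4 states no gate.

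Four stronger readings are tempting and not supported:

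- *The plan inflates the type I error.* At 20% response and 4 active-only dropouts, a single ungated test at 0.05 rejects 3.7% of the time on ITT N and 6.5% on visit n. That is not the plan's error rate, because of the Hochberg steps and the Week 16 gate.
- *Dropout will be heavier on active.* Protocol 5.4 reports five pruritus episodes leading to early treatment termination among 24 subjects in EYP001-202, with no arm given. Stopping treatment is also not the same as having no Week 16 sample. Imbalance is plausible, not established.
- *The removal of zero change was hidden.* Section 15 cites protocol 11.3.3.1 and largely discloses the move to MI. The protocol is itself ambiguous, since the note to its Table 5 ties zero change to the ITT analysis. The gap is that a planned sensitivity analysis is not identified as dropped.
- *The protocol requires missing to count as non-response.* Its denominator has that effect, but it never states the rule. The fix therefore adds a sentence to the protocol's position, and a patient who misses only that visit would count as not meeting the endpoint.

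**Conclusion.** Both parts hold. The four key secondary tables depart from the protocol's ITT denominator without an entry in Section 15, and the SAP leaves the status of a patient without a visit value unwritten. The protocol's zero-change t-test has no counterpart in the SAP, so no planned primary analysis tests reliance on MAR.

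The effect on the key secondary decisions is conditional and modest. It can cross a Hochberg step when dropout is confined to active and the responder count is near a boundary. It did not at about 10% in both arms in these examples, nor for HBsAg loss at the planned rate. These results assume no placebo events, dropouts who are all non-responders, 37:12 allocation, and the inference that the Pearson test follows visit n. The 10% dropout is over the total study duration, so the scenarios fit Week 40 better than Week 16. The documents give no dropout by arm.

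For the primary endpoint, the 86.5% v 79.6% contrast shows what zero change costs in planned power. It does not measure the loss of the sensitivity analysis, which is a loss of information about robustness.

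This should be corrected, but it does not undermine the design.

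**What to change.** - In Tables 14.2.3.1 to 14.2.4.2, replace the footnote with wording such as: *Percentages and the Pearson test use the number of ITT patients in the arm (N); a patient with no HBsAg value at the visit is counted as not meeting the endpoint.* Keep the prespecified Pearson test, and keep the observed-case (visit n) result as a supportive row.
- Reinstate the zero-change t-test at Week 16 as a sensitivity analysis of the primary endpoint.
- In SAP 15, list any denominator that still differs from protocol 11.1, and say that zero change was the protocol's sensitivity t-test and what becomes of it.
- In SAP 2.4, note that zero change there is a sample-size assumption.

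The cost is SAP and shell wording, one row in four shells and one extra table. No new data are needed. The downside is slightly lower reported response rates.
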